## 6.6 Pharmacokinetic, Pharmacodynamics and Immunogenicity Evaluations

### 6.6.1 Pharmacokinetic Evaluation

Pharmacokinetic analyses will be performed on the pharmacokinetic populations and individual serum concentration summary statistics will be computed using all available PK data. All analyses will be performed by dosing regimen.

#### 6.6.1.1 Serum concentrations

A horizontal bar chart titled 'U.S. should take action to address climate change' showing the percentage of respondents who believe the U.S. should take action to address climate change, broken down by age group. The x-axis represents the percentage from 0 to 100. The y-axis lists age groups. The bars are black. The data is as follows:

Age Group	Percentage
18-29	85
30-49	92
50-69	78
70+	82
18-29	75
30-49	88
50-69	72
70+	78
18-29	82
30-49	85
50-69	70
70+	75
18-29	88
30-49	90
50-69	75
70+	80
18-29	80
30-49	85
50-69	70
70+	75
18-29	85
30-49	90
50-69	75
70+	80
18-29	80
30-49	85
50-69	70
70+	75
18-29	85
30-49	90
50-69	75
70+	80
18-29	80
30-49	85
50-69	70
70+	75
18-29	85
30-49	90
50-69	75
70+	80
18-29	80
30-49	85
50-69	70
70+	75
18-29	85
30-49	90
50-69	75
70+	80
18-29	80
30-49	85
50-69	70
70+	75
18-29	85
30-49	90
50-69	75
70+	80
18-29	80
30-49	85
50-69	70
70+	75
18-29	85
30-49	90
50-69	75
70+	80
18-29	80
30-49	85
50-69	70
70+	75
18-29	85
30-49	90
50-69	75
70+	80
18-29	80
30-49	85
50-69	70
70+	75
18-29	85
30-49	90
50-69	75
70+	80
18-29	80
30-49	85
50-69	70
70+	75
18-29	85
30-49	90
50-69	75
70+	80
18-29	80
30-49	85
50-69	70
70+	75
18-29	85
30-49	90
50-69	75
70+	80
18-29	80
30-49	85
50-69	70
70+	75
18-29	85
30-49	90
50-69	75
70+	80
18-29	80
30-49	85
50-69	70
70+	75
18-29	85
30-49	90
50-69	75
70+	80
18-29	80
30-49	85
50-69	70
70+	75
18-29	85
30-49	90
50-69	75
70+	80
18-29	80
30-49	85
50-69	70
70+	75
18-29	85
30-49	90
50-69	75
70+	80
18-29	80
30-49	85
50-69	70
70+	75
18-29	85
30-49	90
50-69	75
70+	80
18-29	80
30-49	85
50-69	70
70+	75
18-29	85
30-49	90
50-69	75
70+	80
18-29	80
30-49	85
50-69	70
70+	75
18-29	85
30-49	90
50-69	75
70+	80
18-29	80
30-49	85
50-69	70
70+	75
18	

Individual serum ARGX-117 concentration data will be listed for each participant and summarized by nominal sampling time point, and visit as applicable with descriptive statistics

Individual serum ARGX-117 concentration-time data will be displayed graphically, summarized and listed.

Serum concentrations below the limit of quantification (BLQ): BLQ values will be flagged as BLQ in the concentration and parameters tables and considered to be 0 for calculation of PK parameters and descriptive statistical analysis. Listings will always present BLQ.

When more than half (>50%) of the values at a single time point are BLQ, the mean, median and minimum values are shown as “BLQ”. The standard deviation (SD) and CV% are not calculated. Maximum values are reported as observed.

The BLQ handling is at the discretion of the PK scientist. Should BLQ handling be different from the above described processes, justification should be given.

[REDACTED]

- [REDACTED]  
[REDACTED]  
[REDACTED]  
[REDACTED] [REDACTED]
- [REDACTED]  
[REDACTED]  
[REDACTED]  
[REDACTED]
- [REDACTED]  
[REDACTED]  
[REDACTED]

Serum concentrations will be summarized by visit, time point and cohort including all scheduled sample assessments except if:

- the predose sample was taken after IMP administration;
- the IMP administration before the scheduled PK sample was missed (not applicable for day 1);
- PK samples are taken outside the visit windows as defined in **Error! Reference source not found..**

#### 6.6.1.2 Pharmacokinetic analyses

Pharmacokinetic analyses will be conducted using the PK set. PK parameters of ARGX-117 will be analyzed based on the actual sampling times. When actual times are not available, nominal times will be used instead if considered appropriate by the pharmacokineticist.

[REDACTED]  
[REDACTED]

The following PK parameters will be calculated for ARGX-117 based on analysis visit:

**Table 16 PK Parameters**

Parameter (Units)	CDISC TERM	Definition	Method of Determination
AUC 0-72h  AUC 0-168h  AUC 0-336h	AUCINT	Area under the concentration versus time curve from 0 to 72 ,0 to 168 h, 0 to 336 h	Calculated using the linear up/log down variant of the trapezoidal rule
C max	C MAX	maximum observed serum concentration	Observed value
C 72h  & C 168h 	C MAX	concentration at 72 h for every week and 168 h for every 2-week dosing after dosing	Observed value
T max	T MAX	time to reach C max	Observed value

[REDACTED]

[REDACTED]

[REDACTED]

[REDACTED]

[REDACTED]

All serum concentration data a will be displayed in listings.

#### PK Outliers

Individual concentration-time points, if considered anomalous, may be excluded from the analysis at the discretion of the PK scientist following a review of the available documentation. Any such exclusion will be discussed with the sponsor and clearly documented in study report. Entire individual treatment profiles for a participant (or for a participant at a specific visit) may be excluded following review of the

available documentation and discussion with the sponsor. However, results of analysis with and without the excluded profiles may be presented in the study report. Any such exclusion will be clearly listed in the study report along with justification for exclusion.

### 6.6.2 Pharmacodynamics Evaluation

Free C2 (mg/L), total C2 (mg/L) and CH50 (Eq/mL) concentrations will be assessed. PD evaluations will be performed based on the PD set

- The actual value, change from baseline, percent change from baseline or each cohort, each day and time point will be summarized using descriptive statistics on IVMP and DBTP on the PD set.

For DBTP only:

- For Free C2, CH50 and Total C2, the maximum percent change from Baseline will be displayed
- Free C2 and CH50, the maximum decrease from baseline and minimum postbaseline value will be derived during DBTP.
- For Total C2, the maximum increase from baseline and maximum postbaseline value will be derived.

For deriving maximum decrease from baseline, minimum post baseline value, maximum increase and maximum postbaseline value all postbaseline nonmissing values will be considered included unscheduled visits.

- PD values expressed as below the quantification limit will be imputed by the value of the quantification limit itself. The LLOQ for Free C2, CH50 and Total C2 are 0.049 mg/L, 0 Eq/mL and 0.78 mg/L respectively.
- PD values expressed as above the quantification limit will be imputed by maximum value of PD parameter or ULOQ itself, if available.

For participants with a baseline PD value below/above the quantification limit, the PD parameter will be excluded from the statistical analysis involving change and percent change from baseline. Listings will always show the non imputed values

- When more than half (>50%) of the values at a single time point are BLQ, the mean, median and minimum values are reported BLQ. The SD, standard error (SE) and CV% are not calculated either. Maximum values are reported as observed.

Any potential impact of missing PD data or exclusion of the parameters from statistical analysis will be evaluated more closely during the data review process. Deviations from the presented calculation methods and data handling rules can be made, based on the discretion of the responsible PK/PD scientist and must be fully justified and documented.

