    - Value at each visit:
      - Hours lost due to absenteeism
      - Hours lost due to presenteeism
      - Total hours lost (absenteeism and presenteeism)
      - Percent of scheduled hours lost due to absenteeism
      - Percent of scheduled hours lost due to presenteeism
      - Percent of total scheduled hours lost (due to absenteeism and presenteeism)

These endpoints will be derived for work-related activities and household chores activities.
- **Endpoints to assess medication treatment satisfaction**
  - Treatment Satisfaction 14-Item Questionnaire for Medication (TSQM-14)
    - For each subscale (Effectiveness, Side effects, Convenience, Overall Satisfaction)
      - Value at each visit of the subscale score
- **Endpoints to assess PK, PD and immunogenicity**

Serum concentrations and PK parameters for ARGX-117:  $AUC_{0-t}$ ,  $AUC_{72h}$ ,  $AUC_{0-168h}$ ,  $AUC_{336h}$ ,  $AUC_{\infty}$ ,  $C_{max}$ ,  $C_{72h}$ ,  $C_{168h}$ ,  $T_{max}$ ,  $t_{1/2}$ ,  $V_z$  and CL

Values, change from baseline and percent change from baseline, maximum percent change from baseline, maximum decrease from baseline (applicable for free C2 and CH50 only), minimum post baseline value (applicable for free C2 and CH50 only), maximum increase from baseline, maximum post baseline value (applicable for Total C2 only) in free C2, total C2, functional complement activity (CH50) over time

- Incidence and prevalence of antidrug antibodies (ADA) against ARGX-117

[REDACTED]

- [REDACTED]  
[REDACTED]
- [REDACTED]

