  - Weight values recorded in pounds will be converted to kilograms using the following formula: kilograms = pounds/2.2046.
  - Height values recorded in inches will be converted to centimeters using the following formula: centimeters = inches\*2.54.
  - Duration on study (weeks) = (last visit date – informed consent date + 1) / 7.
  - Duration on treatment (weeks) = (last IMP intake date – first IMP intake date + 1) / 7.
  - Change from baseline = value at the time point – baseline value.
  - Percent relative change from baseline = [(value at the time point – baseline value) / baseline value] x 100.

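### SAP section 6.6.2 states the CH50 lower limit of quantification as 0 Eq/mL, a value that its own below-limit rules cannot use

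*SAP*

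**What the plan says.** Section 6.6.2 (Pharmacodynamics Evaluation) sets one convention for all three markers: "PD values expressed as below the quantification limit will be imputed by the value of the quantification limit itself". The limits follow: "The LLOQ for Free C2, CH50 and Total C2 are 0.049 mg/L, 0 Eq/mL and 0.78 mg/L respectively". According to the modification history, version 3.0 added these limits because they had been missing for interim analysis 2, so they are the working inputs to the rule.

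Three further parts of the section depend on below-limit status or on the imputed value:

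- **Baseline exclusion:** "For participants with a baseline PD value below/above the quantification limit, the PD parameter will be excluded from the statistical analysis involving change". The same exclusion applies to relative change.
- **Majority display rule:** "When more than half (>50%) of the values at a single time point are BLQ, the mean, median and minimum values are reported BLQ".
- **Extreme-value summaries:** "Free C2 and CH50, the maximum decrease from baseline and minimum postbaseline value will be derived during DBTP". A maximum percent change is also displayed for CH50. Section 3.2 lists these summaries among the secondary endpoints, for example "minimum post baseline value (applicable for free C2 and CH50 only").

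Section 5.2 gives the formula for relative change: "Percent relative change from baseline = [(value at the time point – baseline value) / baseline value] x 100".

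**The concern.** CH50 is the functional complement readout. A lower limit of quantification marks the point below which an assay cannot give a reliable number, so some range must lie beneath it. At 0 there is none, because activity cannot be negative. The figure can be seen to be unusable as a limit from the SAP alone, although the right figure cannot be found there.

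The SAP uses two different conventions. For pharmacokinetics, section 6.6.1.1 sets below-limit concentrations to 0. For pharmacodynamics, section 6.6.2 uses the limit. With a stated limit of 0, CH50 falls back to zero imputation while the text says otherwise, and free C2 and total C2 do not. Low CH50 values are to be expected mainly in the active arms, so setting them to 0 would favour a larger reported pharmacodynamic effect.

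**Working it through.** **Inputs from the SAP.** Limits of 0.049 mg/L (free C2), 0 Eq/mL (CH50) and 0.78 mg/L (total C2); the imputation, baseline-exclusion and majority rules (all section 6.6.2); the percent-change formula (section 5.2). The SAP gives neither a CH50 baseline nor any other CH50 limit, so the values used for them below are assumptions for illustration.

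**Formula.** With baseline b and a value imputed at limit L, percent change = 100 × (L − b)/b = −100 × (1 − L/b).

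**Reading A: below-limit status is a laboratory flag.**

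1. With L = 0 as stated, percent change = 100 × (0 − b)/b = −100% for every positive b.
2. With a positive limit, the same convention gives:

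| L/b (assumed) | Percent change |
|---|---|
| 0.05 | −95% |
| 0.10 | −90% |
| 0.20 | −80% |

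3. A flagged value truly lies between 0 and L, so the true percent change lies between −100% and the figure in the table.
4. The ratio depends on baseline. With an assumed L of 10 Eq/mL, b = 100 gives −90% and b = 40 gives −75%.
5. The baseline exclusion and the majority rule still work, because both can use the flag. If 3 of 5 values are flagged, 60% exceeds 50% and the rule applies.
6. A mean at a time point with 50% or fewer flagged values is not protected. Suppose 40% are flagged, the rest are at −70% and b = 100. The mean is 0.4 × (−100) + 0.6 × (−70) = −82% at L = 0. At assumed limits of 5, 10 and 20 Eq/mL it is −80%, −78% and −74%.
7. The majority rule applies to values at a single time point. The minimum, maximum decrease and maximum percent change are extremes within a participant, so the rule does not cover them. Section 6.6.2 draws the minimum and maximum decrease from all post-baseline values, unscheduled visits included. One flagged sample is enough to give that participant a minimum of 0 and a 100% fall.

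**Reading B: below-limit status is a numeric comparison with 0.**

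1. No CH50 value is below 0. In the set 0, 0, 0, 5, 12, none of the 5 values qualifies.
2. Nothing is imputed, no baseline is excluded as below the limit, and the majority rule never applies.
3. A baseline recorded as 0 therefore stays in, and (value − 0)/0 is undefined. Section 6.5.1.3 has a rule for a zero grip-strength baseline; section 6.6.2 has none for CH50.

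**The case against.** **The SAP has safeguards.** A flagged baseline removes the participant from the change analyses. Heavily suppressed time points show BLQ instead of a mean, median or minimum. Listings keep the non-imputed values. The section also allows documented departures: "Deviations from the presented calculation methods and data handling rules can be made, based on the discretion of the responsible PK/PD scientist". All of this stands, and it narrows the exposure to the participant-level extremes and to time points with 50% or fewer below-limit values. It does not correct the stated figure.

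**Zero may be deliberate.** It could be a slip, a rounded value or the assay's lowest reportable result, and the SAP does not settle which. If the assay reports down to 0 and nothing is expressed as below the limit, the imputation is idle and no imputed value changes. A reader might infer that 0 is simply a typing error; the document does not show that. It shows only that 0 cannot act as a limit in this rule.

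**Two stronger readings are tempting.** One is that every below-limit CH50 becomes a 100% fall and that the other rules also fail. These belong to different readings: under A the fall appears and the other rules work; under B those rules never operate but nothing is imputed. Even under A, the fall applies only to post-baseline values with a quantifiable baseline. The other is that the 5 to 20 point gap is a bias of that size. It is the distance between two imputation conventions: zero can overstate the fall, and the limit can understate it by up to the same amount.

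**Conclusion.** The point holds in this form: the stated CH50 limit of 0 Eq/mL cannot serve in the rule that uses it, and the SAP does not say how below-limit status is decided. The wording about values being expressed as below the limit fits a laboratory flag better. On that reading the consequence is zero imputation for CH50, contrary to the section's own convention, reaching participant-level summaries that the majority rule does not protect. On the numeric reading, the CH50 below-limit rules are empty and a zero baseline is unhandled.

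The size cannot be derived from the SAP. Assuming a true limit of 5% to 20% of baseline, the SAP's convention would show −95% to −80% where the stated figure shows −100%. How many values are affected is unknown.

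The matter is worth correcting but limited in reach. CH50 is a descriptively summarised secondary marker in an exploratory trial without formal hypothesis testing, and the primary endpoints are safety variables.

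**What to change.** In section 6.6.2, replace 0 Eq/mL with the validated CH50 limit from the bioanalytical report, and impute below-limit CH50 with it as for the other two markers. If the assay reports down to 0 with no lower limit, say so, remove CH50 from the below-limit rules and exclude a CH50 baseline of 0 from percent change. In either case, add a sentence stating that below-limit status follows the laboratory flag.

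The cost is one figure and one or two sentences, plus a rerun of the CH50 outputs (Table 14.2.3.5 and the tables by antidrug-antibody class, 14.2.4.9 and 14.2.4.10). The reported maximum reduction in CH50 may come out slightly smaller.

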### 6.6.3 Immunogenicity Evaluation

Blood samples will be collected for the determination of ADA to ARGX-117 (in serum samples) at the time points indicated in the schedule of activities (appendix 9.1).

Immunogenicity samples are analyzed in a 3-tiered approach:

- All samples are evaluated in the ARGX-117 ADA screening assay and are scored screening positive or negative
- If a sample scored screening positive, it is further evaluated in the confirmatory assay and is scored confirmed positive (positive immuno-depletion) or confirmed negative (negative immuno-depletion).
- If a sample is scored as confirmed positive, the samples are further characterized in the titration assay (to determine titer).

[figure not shown]
If available, a titer result will be reported for the ADA confirmed positive samples. However, a titer result is not always available:

- In case the ADA confirmed positive sample could not be run in the titration assay (eg, due to insufficient sample volume/quality to perform the titer analysis), the result will be described as 'positive immuno-depletion' and the sample should be considered as ADA positive.
- If a sample is negative in the titration assay, it will be reported as 'negative titer' but it should be considered as ADA positive since it was confirmed positive in the second tier.
- If a sample could not be analyzed or reported as 'positive screen', the ADA sample status is ADA unevaluable.

An overview of this 3-tiered approach and all possible sample results that will be reported by the laboratory is given below (

Figure 3). From these reported ARGX-117 ADA sample results, a final sample status should be derived during the statistical analysis, as presented in the final column ('Final Outcome'):

**Figure 3 ADA sample status**

a missing screen includes the following terms (reported as reason not performed): NA (not analyzed), NR (no result), NS (no sample) and SL (sample lost). More details are provided in the IS Data Transfer Agreement from Celerion with Cytel.

b 'positive titer' is reported in case it was not possible to retrieve a numeric value.

Table below gives an overview of how the ADA participant classification for ARGX-117 will be derived, starting from the participant baseline ADA sample status.

**Table 17 Participant Classification for ADA Against ARGX-117**

	Highest c post baseline sample status				
Baseline ADA sample status	ADA negative	ADA positive (missing titer a )	ADA Positive (negative titer b or numerical titer value)		ADA Unevaluable
ADA negative	ADA negative	Treatment-induced ADA	Treatment-induced ADA		ADA Unevaluable
ADA positive (missing titer a )	Treatment-Unaffected ADA	ADA Unevaluable	ADA Unevaluable		ADA Unevaluable
ADA Positive (negative titer b or numerical titer value)	Treatment-Unaffected ADA	ADA Unevaluable	titer < 4 x baseline titer: Treatment-Unaffected ADA	titer ≥ 4x baseline titer: Treatment-Boosted ADA	ADA Unevaluable
ADA Unevaluable	ADA Unevaluable	ADA Unevaluable	ADA Unevaluable		ADA Unevaluable

a Samples with missing titer have as reported ADA result ‘positive immuno-depletion’ or ‘positive titer’;

b Results reported as ‘negative titer’, ie, titer value < 100 will be set to 100

c Highest sample status, with order: (from low to high) : ADA unevaluable, ADA negative, ADA positive (missing titer /positive immuno-depletion), ADA positive with titer<100 (‘negative titer’) as reported ADA result, titer value set to 100), ADA positive with titer≥100 (ie, numerical value selecting the sample with highest titer)

**ADA evaluable participant = participant classified as any of following categories according to**

**Table 17:** ADA negative, treatment-unaaffected ADA, treatment-induced ADA, treatment-boosted ADA.  
The first 2 categories are classified as ‘ADA negative’, the latter 2 as ‘ADA positive’.

**ADA unevaluable participant = participant classified as ADA unevaluable according to**

Table 17 or with missing baseline ADA sample or without postbaseline ADA samples

Note: Fourfold difference in titer values is considered significant in case a twofold serial dilution is applied (= 2 times the dilution factor) (reference to Shankar et al., 2014).

The ADA incidence is defined as the percentage of participants with treatment-induced ADAs or treatment-boosted ADAs among the number of evaluable participants.

The ADA prevalence is defined as the percentage of participants with ‘treatment-unaaffected ADA’, ‘treatment-induced ADA’ or ‘treatment-boosted ADA’ among the number of evaluable participants.

ADA analysis will be performed in the SAF set, combining data from DBTP and safety FU.

Frequency tabulations (Number and percentages) will be provided with ADA negative/positive/unevaluable samples per analysis visit and per ADA against ARGX-117 participant classification for each following treatment groups:

- ARGX-117 Dose Regimen 1
- ARGX-117 Dose Regimen 2 [REDACTED] if applicable
- ARGX-117 Dose Regimen 3 [REDACTED] if applicable
- Total ARGX-117
- Total Placebo

Frequency tabulations (Number and percentages) will be provided by treatment group and ARGX-117 combined on:

- Participants per ADA participant classification
- Prevalence and incidence of ADA
- ADA unevaluable participants
- ADA baseline positive / negative / unevaluable samples

ADA titer values against ARGX-117 will be summarized using descriptive statistics by ADA participant classification.

All immunogenicity data will be listed.

Correlation tables by ADA participant classification against ARGX-117 will be provided for the following parameters:

- Serum ARGX-117 concentration over time
- Concentration of free C2
- Percent change from baseline in free C2
- Concentration of total C2
- Percent change from baseline in total C2
- Concentration of CH50
- Percent change from baseline in CH50

- Overall Treatment-Emergent Adverse Events by MedDRA System Organ Class and Preferred Term by Overall Antidrug Antibodies Participant Classification (All Patients)
- Overall Serious Treatment-Emergent Adverse Events by MedDRA System Organ Class and Preferred Term by Overall Antidrug Antibodies Participant Classification (All Patients)
- Overall Treatment-Emergent Hypersensitivity reaction(as defined in the 6.4.1 section) by Overall Antidrug Antibodies Participant Classification (All Patients)
- Overall Treatment-Emergent anaphylactic reaction (as defined in the 6.4.1 section) by Overall Antidrug Antibodies Participant Classification (All Patients)
- Treatment-Emergent Adverse Events of local reactions (as defined in the 6.4.1 section) by Overall Antidrug Antibodies Participant Classification
- Correlation tables on serum ARGX-117 concentration over time will be restricted to the ARGX-117 treated participants only (cohort 1 and cohort 2).

The other correlation tables must be provided for ARGX-117 (ie, cohort 1, cohort 2) and placebo treated participants (ie, total placebo).

[REDACTED]

[REDACTED]

[REDACTED]

[REDACTED]

[REDACTED]

[REDACTED]

[REDACTED]

[REDACTED]

[REDACTED]

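### ADA prevalence drops participants who are confirmed positive at both baseline and post-baseline when a titre is missing, although prevalence does not need the titre

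*SAP*

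**What the plan says.** Section 3.2 of the SAP lists incidence and prevalence of ADA among the secondary endpoints. Section 6.6.3 builds them in three steps.

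- **Sample status.** If a confirmed-positive sample cannot be run in the titration assay, "the sample should be considered as ADA positive".
- **Participant class.** Table 17 crosses the baseline status with the highest post-baseline status. Its footnote a, which begins "Samples with missing titer have as reported ADA result", defines a missing titre as a confirmed positive reported without a usable number. A negative titration result is not a missing titre: footnote b sets it to 100. Participants are unevaluable if Table 17 says so, "or with missing baseline ADA sample or without postbaseline ADA samples".
- **Rates.** Incidence counts treatment-induced and treatment-boosted participants. The sentence that begins "The ADA prevalence is defined as the percentage of participants with" adds the treatment-unaffected class to those two. Both rates are taken "among the number of evaluable participants", so one denominator serves both.

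**The concern.** Incidence needs the titre. Among participants positive at baseline and afterwards, only a fourfold rise separates boosted (counted) from unaffected (not counted). Prevalence asks only whether the participant has ADA. Carrying the incidence denominator over to prevalence therefore removes participants whose samples the SAP itself calls positive.

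The rule also works backwards in one place. A participant with an untitred positive baseline who is negative afterwards is "Treatment-Unaffected ADA" and counts in prevalence. With the same baseline and a positive sample afterwards, the participant is dropped. More evidence of ADA takes the participant out of the figure.

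At stake is a named secondary endpoint in small arms, where one participant can move the percentage by several points.

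**Working it through.** **Step 1: the missing-titre cells.** Table 17 has five combinations in which both samples are evaluable, at least one is positive, and a titre is missing.

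| Baseline | Highest post-baseline | Table 17 class | In prevalence? |
|---|---|---|---|
| negative | positive, no titre | induced | yes |
| positive, no titre | negative | unaffected | yes |
| positive, no titre | positive, no titre | unevaluable | no |
| positive, no titre | positive, titre | unevaluable | no |
| positive, titre | positive, no titre | unevaluable | no |

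Two are counted and three are dropped. In each of the three, the only open question is unaffected versus boosted, and both belong to the prevalence numerator.

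**Step 2: direction.** Let N be the number evaluable under the SAP, P the number of those counted as ADA positive, and u the number dropped from the three cells. The SAP reports P/N. Restoring the dropped participants gives (P + u)/(N + u). The difference is

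(P + u)/(N + u) − P/N = u(N − P) / [N(N + u)].

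This is never negative. It is zero only if u = 0 or if every evaluable participant is positive (P = N). No ADA-negative participant can fall into these cells, so nothing offsets the loss.

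**Step 3: size.** The SAP states no prevalence and no missing-titre rate, so there is no figure to reproduce. The arm size of 16 is from section 6.1; P and u are assumptions. All other participants are taken as evaluable, so N = 16 − u.

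| P | u | SAP rule | Restored |
|---|---|---|---|
| 2 | 0 | 2/16 = 12.5% | 2/16 = 12.5% |
| 1 | 1 | 1/15 = 6.7% | 2/16 = 12.5% |
| 2 | 1 | 2/15 = 13.3% | 3/16 = 18.8% |
| 2 | 2 | 2/14 = 14.3% | 4/16 = 25.0% |
| 4 | 1 | 4/15 = 26.7% | 5/16 = 31.3% |

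For P = 2 and u = 1 the formula gives 1 × 13/(15 × 16) = 5.4 percentage points, which matches the third row.

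**Step 4: missing or unevaluable samples, for contrast.** This exclusion removes participants whether their remaining sample is positive or negative. Again with 16 in the arm and assumed counts:

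- 2 counted, 1 positive and 1 negative dropped: 2/14 = 14.3% under the SAP, 3/16 = 18.8% if both are restored.
- 4 counted, 1 positive and 3 negative dropped: 4/12 = 33.3% under the SAP, 5/16 = 31.3% if all are restored.

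The direction can go either way. If samples are lost independently of ADA status, the expected prevalence does not change.

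**The case against.** The case for leaving the text alone has several parts.

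- **Sample status and participant class are different things.** The statement that an untitred sample is positive governs the by-visit sample tabulations, and Table 17 governs participants. This stands, so there is no formal contradiction. It does not explain why prevalence should need a titre.
- **The cells may be rare.** They require ADA before any IMP. Under footnote c a titred positive outranks an untitred one, so the cell with a titred baseline arises only if every post-baseline positive lacks a titre. This stands for that cell. It does not help a participant whose baseline sample is untitred: any later positive leads to exclusion.
- **The exclusions are visible.** Section 6.6.3 tabulates unevaluable participants and lists all immunogenicity data. But the planned count does not separate confirmed positives lacking a titre from participants with no usable data, so the tables alone do not let a reader correct the prevalence.
- **One denominator for both rates is convenient, and the study is exploratory.** Both are true. They keep the point modest but do not justify an exclusion with a known direction.

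A reader might infer more: that any missing titre, or any missing baseline or post-baseline sample, makes the reported prevalence too low. The SAP does not support that. Two of the five missing-titre combinations are counted, including a baseline-negative participant with an untitred later positive, classed as "Treatment-induced ADA". The missing-sample rule removes negatives as well as positives, so its net effect has no fixed sign. Nor should the denominator simply become everyone with at least one evaluable sample: a participant with only a negative baseline sample would then count as ADA-free without having been observed on treatment.

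**Conclusion.** The point holds for three cells of Table 17: confirmed positive at both baseline and post-baseline, with a titre missing on either side. Excluding these participants from prevalence serves no purpose and can only lower the figure, unless no evaluable participant is negative or no titre is missing. The direction follows from the definitions alone. The size rests on counts that the SAP does not give. In the assumed case of 16 per arm and 2 counted positives, one such participant makes a difference of 5.4 percentage points. Incidence is unaffected, and the use of Table 17 there is sound. This is a modest correction to a descriptive secondary endpoint.

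**What to change.** In section 6.6.3, keep Table 17 and its evaluable set for incidence and for the split between unaffected and boosted. Add one sentence for prevalence only: participants confirmed ADA positive at both baseline and post-baseline are included in numerator and denominator whatever their titre status. Show them as their own row, for example *ADA positive, not classifiable for boosting*. Keep that row apart from the SAP's participant-level ADA-positive group, which means induced or boosted.

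Leave participants with a missing or unevaluable baseline or post-baseline status out of the main prevalence. A sensitivity prevalence that includes those with one evaluable time point may be added if its denominator is stated.

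The cost is one sentence and one derived flag. Prevalence and incidence will have slightly different denominators whenever such participants occur, so each needs its denominator printed, and prevalence may look slightly less favourable.
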